**Analysis of the Secondary Endpoint(s)**

*Efficacy Endpoints:*

For Proportion of subjects with the IGA score of 0 or 1.

Change from baseline of target lesion area(s), change from baseline in pruritus NRS of itch level on target lesion area(s), change from baseline in signs of atopic dermatitis (erythema, edema/papulation, excoriation and lichenification) on target lesion area(s), and change from baseline in the total score of the POEM will be analyzed by using descriptive statistics, p-value of Wilcoxon sign-rank test or paired-t test will be given to test the improvement.

Frequency tables of change from baseline will be presented for pruritus NRS of itch level, and

the total score of the POEM as appropriate.

### **Safety Analyses**

Adverse events will be coded by employing Medical Dictionary for Regulatory Activities (MedDRA). The version of MedDRA used for coding should be agreed by sponsor before coding starts. AE will be displayed by subject count, i.e. each subject is counted only once within each category of AE. The incidence of AEs will be presented by System Organ Class (SOC) and preferred term groupings. For Phase I, incidence of DLT will be presented on both ITT population and evaluable subjects. The information of AEs, such as start date, stop date, severity, relationship, expectedness (only for SAE), outcome, and duration, should be listed. Adverse events leading to premature discontinuation from the study intervention and serious adverse events (SAEs) should be presented either in a table or a listing.

Findings in physical examinations will be displayed for each individual system. Findings in ECG will be tabulated with transition from baseline. Net changes from baseline laboratory parameters, weight and vital signs will be analyzed by using descriptive statistics with p-value of Wilcoxon sign-rank test or paired-*t* test given. The baseline is defined as the closest test result prior to the first dosing of AR100DP1 topical administration.

5. Planned interim analysis:  yes  no

Interim analysis will be performed upon the completion of Phase I study.

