**VI. Endpoints:**

**1. Primary endpoint(s):**

**Phase I:** Determine the MTD of AR100DP1

*MTD is defined as the highest dose level at which < 2 of 6 subjects experienced a dose limiting toxicity (DLT) during Visit 2-6 (DLT observation period).*

**Phase IIa:** Proportion of subjects with the Investigator's Global Assessment (IGA) score of 0 or 1 on Day 29.

**2. Secondary endpoint(s):****Phase I:**Safety:

- Incidence of adverse events (AE) and serious adverse events (SAE) during Visit 2-6
- Change from baseline in vital signs at Visit 2-6
- Abnormality in physical examination at Visit 2-6
- Transition from baseline in electrocardiogram (ECG) result at Visit 3-6
- Change from baseline in laboratory parameters at Visit 3-6

**Phase IIa:**Efficacy:

- Proportion of subjects achieving the Investigator's Global Assessment (IGA) score of 0 (clear) or 1 (almost clear) on Day 8, Day 15, Day 22, Day 36 and Day 43
- Change from baseline of target lesion area(s) on Day 8, Day 15, Day 22, Day 29, Day 36, and Day 43
- Change from baseline in pruritus NRS of itch level on target lesion area(s) on Day 8, Day 15, Day 22, Day 29, Day 36 and Day 43
- Change from baseline in signs of atopic dermatitis (erythema, edema/papulation, excoriation and lichenification) with grading from 0 (none) to 3 (severe) on target lesion area(s) on Day 8, Day 15, Day 22, Day 29, Day 36 and Day 43
- Change from baseline in the total score of the Patient-Oriented Eczema Measure (POEM) on Day 8, Day 15, Day 22, Day 29, Day 36 and Day 43

Safety:

- Incidence of AE and SAE during Visit 2-8
- Change from baseline in vital signs at Visit 2-8
- Abnormality in physical examination at Visit 2-8
- Transition from baseline in ECG result at Visit 3-8
- Change from baseline in laboratory parameters at Visit 3-8

Exploratory:

- Fold change of IgE on Day 15 and Day 29 compared to baseline on Day 1 ( $IgE_{D15}/IgE_{D1}$ ,  $IgE_{D29}/IgE_{D1}$ )
- Fold change of IL-4 on Day 15 and Day 29 compared to baseline on Day 1 ( $IL-4_{D15}/IL-4_{D1}$ ,  $IL-4_{D29}/IL-4_{D1}$ )

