### The following exclusion criteria are applied for all subjects in Phase I/IIa study:

- (5) Plan to receive immunosuppressive agents (including azathioprine, mycophenolate, cyclophosphamide, chlorambucil, methotrexate, cyclosporine), or systemic steroid with equivalent dosage higher than prednisolone 30 mg/day for more than 14 days at Screening
- (6) Unwilling or unable to comply with the criteria in Life Style Guidelines (Section IX 1.) during the study
- (7) History of use of biologic therapy (including intravenous immunoglobulin) within 12 weeks or 5 half-lives (whichever is longer) prior to Screening
- (8) Received any other investigational drug within 4 weeks prior to Screening

- (9) Required or received systemic CYP3A4 inhibitors with strong potency within 1 week prior to screening, including but not limited to clarithromycin, itraconazole, nefazodone and atazanavir, evaluated by the investigator
- (10) Treatment for any type of cancer (except squamous cell carcinoma, basal cell carcinoma, or carcinoma in situ of the skin, curatively treated with cryosurgery or surgical excision only) within 5 years before screening
- (11) Had surgery within 4 weeks prior to Screening Visit, or plan to have surgery during the study
- (12) Allergies requiring acute or chronic treatment at the investigator's discretion
- (13) Known hypersensitivity to any of the components of the study drug
- (14) Active clinically serious infection or history of human immunodeficiency virus (HIV) infection
- (15) Any of the following serum test abnormalities:
  - Total bilirubin  $> 1.5 \times$  ULN
  - AST or ALT  $> 3.0 \times$  ULN
  - Serum albumin  $< 2.5 \text{ g/dL}$
  - Creatinine  $> 1.5 \times$  ULN
  - Any other  $\geq$  Grade 2 (grading of vaccine clinical trials for Phase I and NCI-CTCAE v5.0 for Phase IIa) laboratory abnormality at baseline (other than those listed above)
- (16) With ongoing acute diseases or within the past 2 years serious medical conditions (e.g. concomitant illness) such as cardiovascular (e.g. New York Heart Association (NYHA) grade III or IV), hepatic (e.g. Child-Pugh Class C), psychiatric condition (e.g. alcoholism, drug abuse), medical history, physical findings, or laboratory abnormality that in the investigators' opinion could interfere with the results of the trial or adversely affect the safety of the subject
- (17) Female subject who is lactating or has positive urine pregnancy test at screening

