## X. Statistics:

1. **Primary hypothesis:**  superiority  non- inferiority  equivalence  other
2. **Sample size:** Enrolled 35 subjects (Phase I: 21 subjects/Phase IIa: 14 subjects)  
Evaluable 30 subjects (Phase I: 18 subjects/Phase IIa: 12 subjects)
3. **Efficacy population:**  ITT  PP (Phase IIa only)  Other (PP-EOT, Phase IIa only)

**Safety population:**  ITT  PP  Other (MTD, Phase I only)

Intent-to-treat (ITT) population:

- Enrolled subjects receiving at least one dose of AR100DP1

MTD population (Phase I Only):

- Eligible subjects who administered at least one dose of the investigational product and experienced DLT
- OR
- Eligible subjects who were dosed for at least 12 days with at least 85% of compliance.

Per-protocol before End of Treatment (PP-EOT) population (Phase IIa Only):

- A subset of ITT population
- Fulfill all inclusion and exclusion criteria
- Subjects dosed for at least 21 days of Phase IIa with at least 75% of compliance
- No major protocol deviation which could affect the efficacy assessment

- Not take any prohibited therapy before End of Treatment (EOT) Visit assessment

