**Per-protocol (PP) population (Phase IIa Only):**

- A subset of PP-EOT population
- Not take any prohibited therapy during the study

Efficacy analysis will be conducted in ITT, PP-EOT and PP population for Phase IIa study.

Demographic, baseline characteristics and safety analyses will be conducted in ITT population for both Phase I and Phase IIa studies. Efficacy results for Phase IIa study will be concluded in ITT population.

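### The laboratory safety p-value tests a group shift, and no table is specified that counts the subjects whose laboratory values become abnormal

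*Combined protocol and SAP*

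**What the plan says.** All references are to the synopsis in the combined protocol and SAP.

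- **Endpoint (section VI, Phase IIa safety).** "Change from baseline in laboratory parameters at Visit 3-8". Phase I has the same endpoint for Visits 3 to 6.
- **Analysis (section X.4, Safety Analyses).** "Net changes from baseline laboratory parameters, weight and vital signs will be analyzed by using descriptive statistics with p-value of Wilcoxon sign-rank test". The sentence goes on to allow a paired t test instead, and does not say which test applies when.
- **ECG (same paragraph).** "Findings in ECG will be tabulated with transition from baseline". No such table is specified for laboratory parameters.
- **Population (section X.3).** "Demographic, baseline characteristics and safety analyses will be conducted in ITT population for both Phase I and Phase IIa studies". ITT means enrolled and dosed at least once.
- **Size (section X.2).** "Enrolled 35 subjects (Phase I: 21 subjects/Phase IIa: 14 subjects") and "Evaluable 30 subjects (Phase I: 18 subjects/Phase IIa: 12 subjects").
- **Grading (section VII.2, exclusion (15)).** A laboratory grading scale is named for each phase: "grading of vaccine clinical trials for Phase I and NCI-CTCAE v5.0 for Phase IIa". The same criterion sets numerical limits for bilirubin, AST/ALT, albumin and creatinine.
- **Other output.** General Approach lists the minimum and maximum among the summary statistics. Safety Analyses counts adverse events by subject and lists their severity and relationship.

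**The concern.** For liver enzymes, bilirubin, creatinine and blood counts, the safety question is whether any subject moves into an abnormal range, how far, and from what starting point. A signed-rank or paired t test has a different null hypothesis: no location shift across the group. An effect confined to a few subjects can be large in each of them and still leave that null unrejected.

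Safety in subjects with atopic dermatitis is a secondary objective of Phase IIa, and the trial is first-in-human. With about 14 subjects, a plausible signal is one to three people becoming abnormal, which is where these tests are weakest. Two things are at stake: a non-significant p-value may be read as reassurance, and the plan specifies no table giving the number of subjects who became abnormal.

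**Working it through.** The plan gives no power, alpha or critical value for these tests, so there is no stated figure to reproduce. The sample-size totals agree: 21 + 14 = 35 and 18 + 12 = 30.

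**Inputs.** From the documents: n = 14 (Phase IIa enrolled), with n = 12 (evaluable) as a check. Assumed: two-sided 0.05, with one-sided 0.05 shown as the range. The size of the rise and the variation in other subjects are also assumed.

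**1. Paired t, k subjects rise by d and n−k do not change.** The mean change is kd/n and the variance is d²k(n−k)/[n(n−1)]. Hence t = √[k(n−1)/(n−k)] on n−1 degrees of freedom. The size d cancels.

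**2. Exact signed-rank, same data, zeros dropped.** Two-sided p = min(1, 2/2^k).

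For n = 14 (critical t = 2.16 two-sided, 1.77 one-sided):

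| k | t | paired t, two-sided p | signed-rank, two-sided p |
|---|---|---|---|
| 1 | 1.00 | 0.34 | 1.00 |
| 2 | 1.47 | 0.16 | 0.50 |
| 3 | 1.88 | 0.082 | 0.25 |
| 4 | 2.28 | 0.040 | 0.125 |
| 5 | 2.69 | 0.019 | 0.0625 |
| 6 | 3.12 | 0.008 | 0.031 |

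The last non-significant k is 3 for the paired t and 5 for the exact signed-rank test.

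**3. Sensitivity of these limits.**
- n = 12: at k = 3 the paired t gives p = 0.082 and at k = 4 p = 0.039, so the limit is again 3. The signed-rank p depends only on k.
- Signed-rank with the k rises holding the top ranks and the other subjects balanced around zero (n = 14): p = 0.241 at k = 3, 0.058 at k = 5, 0.030 at k = 6. The limit stays at 5.
- Signed-rank with Pratt's handling of zeros (normal approximation): p = 0.084 at k = 3, 0.046 at k = 4. The limit falls to 3.
- One-sided 0.05, k = 3: paired t p = 0.041, which is significant; signed-rank p = 0.125, which is not.

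**4. Variation in every subject.** Simulation with n = 14, N(0,1) changes, k subjects raised by a fixed multiple of the SD, 100,000 runs per setting. Percentage of runs with two-sided p < 0.05:

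| k | test | 3 SD | 5 SD | 10 SD | 20 SD |
|---|---|---|---|---|---|
| 3 | paired t | 17.5 | 18.3 | 11.1 | 1.6 |
| 3 | signed-rank | 15.4 | 15.9 | 15.9 | 15.9 |
| 4 | paired t | 33.7 | 45.2 | 61.5 | 80.9 |
| 4 | signed-rank | 26.4 | 27.5 | 27.7 | 27.6 |

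With three affected subjects, both tests miss in more than four runs out of five. Under a one-sided 0.05 paired t, the k = 3 rejection rate would instead be 35%, 45%, 60% and 78%.

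**5. What a count would show.** Three of 14 is 21.4% (exact 95% CI 4.7% to 50.8%). Zero of 14 gives a one-sided 95% upper bound of 1 − 0.05^(1/14) = 19.3%. Either statement addresses the safety question directly.

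**The case against.** **The p-value is not the only laboratory output.** This stands. The maximum is reported, and in 14 subjects a 10 SD rise would be plain in the maximum and the SD. Adverse events are recorded at every visit and counted by subject, and a laboratory abnormality is a named ground for withdrawal. A reader might infer that the plan would hide laboratory toxicity; the documents do not support that. The cover is partial, however. A maximum describes one subject and does not say how many crossed a limit or from what baseline. Baseline matters because exclusion (15) admits AST/ALT up to 3.0 × ULN and bilirubin or creatinine up to 1.5 × ULN. A laboratory rise enters the adverse event tables only if someone records it as an adverse event.

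**The p-values carry no alpha, sidedness or decision rule.** This also stands, and it limits the severity. A reader might infer that three affected subjects must give a non-significant result. That is too strong: the limit of 3 is for a two-sided paired t with everyone else unchanged, noise gives some rejections, and a one-sided paired t is already significant at 3 of 14.

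**Larger rises do not always weaken the paired t.** Correct. For k = 3 the rejection rate falls at very large rises, but for k = 4 it climbs with their size.

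**The text is a synopsis, and ECG results are categorical while laboratory values are continuous.** A synopsis may omit table detail, so its silence does not prove that no shift table would be produced. But it does state a laboratory method, and that method addresses the group. The grading scales are named there for eligibility rather than for on-treatment tables, yet they show that a way to categorise the values is already at hand.

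**Conclusion.** The point holds as a mismatch between the safety question and the stated analysis. At two-sided 0.05 (assumed) and with the other subjects unchanged, large equal rises are non-significant in up to 3 of 14 subjects by paired t and up to 5 of 14 by the exact signed-rank test. With ordinary variation and three affected subjects, non-significance is the usual result, not a certain one: p < 0.05 in about 2% to 18% of runs (paired t) and 15% to 16% (signed-rank) for rises of 3 to 20 SD. These SD multiples are illustrative, since the documents give no laboratory variability.

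Severity is minor to moderate. The data are collected and partly visible elsewhere, and no endpoint, dose decision or conclusion is tied to these p-values. What is missing is a specified count of subjects who became abnormal, and protection against reading a non-significant p-value as safety.

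**What to change.** In section X.4 (Safety Analyses) and in the safety endpoints of section VI, for both phases:

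1. Add a per-subject table of baseline grade against worst post-baseline grade for each laboratory parameter, using the scale that exclusion (15) already names for that phase.
2. Add the number of subjects newly beyond the exclusion (15) limits for bilirubin, AST/ALT, creatinine and albumin. Blood counts have no numerical limit there, so they are covered by the grade table only.
3. Base the laboratory safety summary on these tables, and keep the descriptive statistics of change as support.
4. Drop the paired p-values for laboratory parameters, or state beside them that a non-significant value is not evidence of safety.

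This is a reporting change. It uses results already scheduled and needs no extra visits, samples or subjects. The cost is an edit to the wording and slightly more programming.

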### **XI. Please attach flow chart and/or assessment schedule, if available:**

#### **Phase I**

Procedures/Assessments	Screening	Study Period					Unscheduled	
		Treatment		Follow-up	Final m			
Visit	1	2 f	3 *	4 EOT k	5	6	Early Termination (ET l ) Visit	Unscheduled Visit (UV) during Study Period a
Day	-14 - -1	1	8	15	22	29		
Window period (days)	-	-	± 1	± 2	± 3	± 3		
Informed consent	X							
Identifier number	X							
Demographics	X							
Medical history	X							
Medication history	X							
Eligibility	X	X g						
Pregnancy test b	X			X		X	X	X
Vital signs	X	X g,h	X	X	X	X	X	X
Weight & height i	X					X	X	

Physical examination	X	X g,h	X	X	X	X	X	X
ECG c	X	X g	X	X	X	X	X	X
Laboratory test d,e	X		X	X	X	X	X	X
Recording of the test skin area(s) g		X						
IP administration at site		X h						
Dispense diary and IP j		X	X					X
Retrieve diary and IP j			X	X			X	X
Concomitant medications	X	X	X	X	X	X	X	X
Adverse event	X	X	X	X	X	X	X	X

## Note:

- \* On the days of scheduled visits, subjects are advised to have NO IP administration prior to completion of scheduled assessments.
- a. Unscheduled visits and actions at the visit will be arranged at the investigator's discretion.
- b. Pregnancy tests performed within 2 days before each designated visit will be acceptable.
- c. ECG tests performed within the window period and prior to each designated visit (Visit 3-6) will be acceptable.
- d. Laboratory tests performed within 7 days before Screening Visit and within 2 days before other visits will be acceptable.
- e. Laboratory tests include hematology (hemoglobin, hematocrit, RBC, platelet, WBC with differential counts) and biochemistry (total bilirubin, AST, ALT, serum creatinine, albumin).
- f. The eligibility check at Visit 2 will be based on the results of pre-treatment measurements scheduled at Visit 2, accompanying with other information obtained at Visit 1 before IP administration at the study site.
- g. Procedures to be performed before IP administration.
- h. Subjects will be observed for at least 30 minutes for vital signs and physical exam again after AR100DP1 topical administration at the study site. IP will be applied for twice on Day 1 regardless if the visit is at AM or PM.
- i. The height is only measured at Screening Visit.
- j. The weight of IP will be recorded when dispensing and returning. Actions scheduled on unscheduled visit are optional.
- k. EOT, end of treatment, means the visit right after the treatment period is completed.
- l. ET, early termination, is defined as the decision of withdrawal is made prior to Visit 4. Subjects will be requested to complete the coming scheduled visit as ET Visit within 7 days after the last dose.
- m. When the decision of withdrawal is made after the treatment period (Visit 4, EOT) has been completed, subjects should come back for the assessments at Final Visit within 7 days after the decision is made.

**Phase IIa**

Procedures/ Assessments	Screening	Study Period							Unscheduled	
		Treatment					Follow-up	Final m		
Visit	1	2 f	3*	4*	5*	6 EOT k	7	8	Early Termination (ET l ) Visit	Unscheduled Visit (UV) during Study Period a
Day	-14 ~ -1	1	8	15	22	29	36	43		
Window period (days)	-	-	± 1	± 2	± 2	± 2	± 3	± 3		
Informed consent	X									
Identifier number	X									
Demographics	X									
Medical history	X									
Medication history	X									
Eligibility	X	X g								
Pregnancy test b	X					X		X	X	X

Vital signs	X	X g,h	X	X	X	X	X	X	X	X
Weight & height i	X							X	X	
Physical examination	X	X g,h	X	X	X	X	X	X	X	X
ECG c	X	X g	X	X	X	X	X	X	X	X
Laboratory test d,e	X		X	X	X	X	X	X	X	X
IGA score	X	X g	X	X	X	X	X	X	X	X
Pruritus NRS on target lesion area(s)		X g	X	X	X	X	X	X	X	X
Signs of atopic dermatitis on target lesion area(s)		X g	X	X	X	X	X	X	X	X
POEM score		X g	X	X	X	X	X	X	X	X
Immune response (IgE, IL-4)		X g		X		X			X	X
Selection, measuring, and recording of target lesion area(s) n	X	X g	X	X	X	X	X	X	X	X
IP administration at site		X h								
Dispense diary and IP j		X	X	X	X					X
Retrieve diary and IP j			X	X	X	X			X	X
Concomitant medications	X	X	X	X	X	X	X	X	X	X
Adverse event	X	X	X	X	X	X	X	X	X	X

## Note:

- \* On the days of scheduled visits, subjects are advised to have NO IP administration prior to completion of scheduled assessments.
- a. Unscheduled visits and actions at the visit will be arranged at the investigator's discretion.
- b. Pregnancy tests performed within 2 days before each designated visit will be acceptable.
- c. ECG tests performed within the window period and prior to each designated visit (Visit 3-8) will be acceptable.
- d. Laboratory tests performed within 7 days before Screening Visit and within 2 days before other visits will be acceptable.
- e. Laboratory tests include hematology (hemoglobin, hematocrit, RBC, platelet, WBC with differential counts) and biochemistry (total bilirubin, AST, ALT, serum creatinine, albumin).
- f. The eligibility check at Visit 2 will be based on the results of pre-treatment measurements scheduled at Visit 2, accompanying with other information obtained at Visit 1 before IP administration at the study site.
- g. Procedures to be performed before IP administration.
- h. Subjects will be observed for at least 30 minutes for vital signs and physical exam again after IP administration at the study site. IP will be applied for twice on Day 1 regardless if the visit is at AM or PM.
- i. The height is only measured at Screening Visit.
- j. The weight of IP will be recorded when dispensing and returning. Actions on unscheduled visit are optional.
- k. EOT, end of treatment, means the visit right after the treatment period is completed.
- l. ET, early termination, is defined as the decision of withdrawal is made prior to Visit 6. Subjects will be requested to complete the coming scheduled visit as ET Visit within 7 days after the last dose.
- m. When the decision of withdrawal is made after the treatment period (Visit 6, EOT) has been completed, subjects should come back for the assessments at Final Visit within 7 days after the decision is made.
- n. Selection is only executed at Screening. Measuring and recording are executed at every visit.
